15.2.3 Adverse Events Leading to Discontinuation / Dose Reduction of Study Treatment

The frequency (number and percentage) of participants with each of the following will be presented in a summary table:

- TEAEs leading to temporary discontinuation of study treatment (any study treatment and by study treatment components)
- Study treatment related TEAEs leading to temporary discontinuation of study treatment (any study treatment and by study treatment components)
- TEAEs leading to permanent discontinuation of study treatment (any study treatment and by study treatment components)
- Study treatment related TEAEs leading to permanent discontinuation of study treatment (any study treatment and by study treatment components)
- TEAEs leading to dose reduction of study treatment (any study treatment and by study treatment components)
- Study treatment related TEAEs leading to dose reduction of study treatment (any study treatment and by study treatment components)

In addition, tables summarizing the frequency of participants with AEs, presented by SOC and PT, in the above categories will be prepared. Tables summarizing TEAEs related to study treatment will be created to summarize TEAEs related to any study treatment and will be repeated to summarize TEAEs related to specific study treatment components (i.e. tepotinib and osimertinib).

Actions that can be taken by the Investigator to address an Adverse Event are collected by sections "Action(s) taken with Tepotinib" and "Action(s) taken with Osimertinib" on the "Adverse Events

Details" eCRF page. It is possible that a TEAE leads to more than one action: for example, a drug interruption followed by drug withdrawal. In this case, the TEAE will be counted among the TEAEs leading to temporary discontinuation as well as among the TEAEs leading to permanent discontinuation.

Participant listings showing the relevant information will also be provided:

- AEs leading to permanent discontinuation of study treatment
- AE leading to temporary discontinuation of study treatment

In case the AE leading to temporary or permanent discontinuation of study treatment is composed of several episodes with different toxicity grades or other characteristics, all the occurencies of this AE will be listed.

15.3 Deaths, Other Serious Adverse Events, and Other Significant Adverse Events

15.3.1 Deaths

Deaths from both Period 1 and Period 2 (see Table 3), deaths within 30 days after last dose of study treatment, deaths within 60 days after the first dose of study treatment, as well as reason for death, will be tabulated based on information from the "Death" eCRF page.

- Number of deaths overall and by primary reason
- Number of deaths within 30 days after the last dose of study treatment overall and by primary reason
- Number of deaths within 60 days after the first dose of study treatment overall and by primary reason

Primary reasons for death can be:

- Progressive disease and/or disease related condition
- Event unrelated to tepotinib and osimertinib
- Event related to tepotinib
- Event related to osimertinib
- Event related to tepotinib and osimertinib
- Unknown
- Missing

In addition, the date and cause of death will be provided in an individual participant data listing together with selected dosing information (date of first / last administration). This listing will also include:

• AEs with fatal outcome (list preferred terms of AEs with outcome=fatal)

- Flag for death within 30 days of last study treatment
- Flag for death within 60 days of first study treatment

Deaths that occured during Period 2 will be flagged.

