8.1.2 Analyses per Analysis Set

The following table summarizes the use of the analysis sets and the groups specified above to present the results of the different analysis in tables and figures.

Table 1. Analysis Sets: presentation of the results in tables and figures

Analysis	Analysis set	Results to be presented by
Baseline Characteristics, Baseline Biomarkers, Protocol Deviations, Previous or Concomitant Medications/Procedures	SAF	Tepotinib RP2Dmg + Osimertinib 80mg: T+, L+, Combined (T+ and/or L+), Other, Total Tepo+Osi Tepotinib 500mg: T+, L+, Combined (T+ and/or L+), Other, Total Tepo Total

Analysis	Analysis set	Results to be presented by
Efficacy (excluding sensitivity analyses, subgroup analyses, overall survival and QoL): primary and secondary endpoints	mFAS	Tepotinib RP2Dmg + Osimertinib 80mg: T+, L+, Combined (T+ and/or L+) Tepotinib 500mg: T+, L+, Combined (T+ and/or L+)
Efficacy (sensitivity analysis: start of subsequent anti-cancer treatment, study treatment discontinuation due to COVID-19, subgroup analyses, overall survival and QoL only): primary and some secondary endpoints	mFAS	Tepotinib RP2Dmg + Osimertinib 80mg: T+, L+, Combined (T+ and/or L+)
Efficacy (sensitivity analysis: all participants in the FAS): primary endpoint and some secondary endpoints	FAS	Tepotinib RP2Dmg + Osimertinib 80mg Tepotinib 500mg
Efficacy (Central Nervous System Tumor Response based on RANO- BM criteria): tertiary/exploratory endpoints	FAS/mFAS	Tepotinib RP2Dmg + Osimertinib 80mg: T+, L+, Combined (T+ and/or L+), Other, Total Tepo+Osi (as applicable according to whether FAS or mFAS is presented)
Safety: primary endpoint for the safety run-in	SRIAS	Tepotinib 500mg + Osimertinib 80mg
Safety: all other safety endpoints; Compliance and Exposure	SAF	Tepotinib RP2Dmg + Osimertinib 80mg: T+, L+, Combined (T+ and/or L+), Other, Total Tepo+Osi Tepotinib 500mg: T+, L+, Combined (T+ and/or L+), Other, Total Tepo
Listings (excluding enrollment)	SAF or FAS	SAF for listings presenting baseline and safety data FAS for efficacy listings

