9.2 Study Day / Study Treatment Day

In this IAP, "study treatment" comprises tepotinib and osimertinib in the combination arm and indicates tepotinib only in the monotherapy arm; "study treatment component" will be used to refer to each study drug separately.

Day 1 is the day of the start of study treatment, the day before is Day -1 (no Day 0 is defined). Study day / Study treatment day is defined relative to Day 1.

Study treatment start date:

For each participant, the study treatment start date is the date of first administration of the study treatment (for the combination arm, it will be the earliest date between the two study treatment components; for the monotherapy arm it will be the date of the first administration of tepotinib).

Study treatment end date:

For each participant in the combination arm, the study treatment end date is the date of the last administration of the study treatment (for the combination arm, it will be the latest date between

29/94

the two study components; for the monotherapy arm it will be the last date of administration of tepotinib as monotherapy).

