9.3 Definition of On-treatment Periods

Participants in the monotherapy arm will be allowed to switch to the combination treatment once PD is confirmed. The following on-treatment periods are defined in order to indicate which data will be used for the analyses.

Table 3.	On-treatment Periods
----------	-----------------------------

		Combination Arm	Monotherapy Arm - No Switch	Monotherapy Arm – Switch ^a
Period 1	Start	First dose of study treatment	First dose of study treatment	First dose of study treatment
	End	Last dose of study treatment + 30 days or the cut-off date or death, whichever occurs first	Last dose of study treatment + 30 days or the cut-off date or death, whichever occurs first	First dose of osimertinib ^b
Period 2	Start	NA	NA	First dose of osimertinib ^b
	End	NA	NA	Last dose of combination treatment ^c + 30 days or the cut-off date or death, whichever occurs first

a: Unless stated otherwise, data from Period 1 will contribute to tables, figures and listings whereas data from Period 2 to study discontinuation will only be listed.

b: Measurements collected on the day of the start of the combination treatment will be considered to belong to Period 1 unless clearly collected after the first administration of osimertinib. The same rule applies to adverse events.

c: The last dose of the combination treatment is considered as the last dose of tepotinib or osimertinib, whichever is later.

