- if creatinine clearance (Cockcroft-Gault) is not measured at screening and/or the reference ranges are not available, the reference ranges reported in Section 18.3 will be used for all the collected or derived values.

The derived creatinine clearance will be analysed and presented as a non-gradable parameter in tables and listings. The creatinine clearance values collected only at the screening visit and reported in the eCRF will only be listed.

Calcium

Total calcium, corrected calcium and ionized calcium will be collected in the eCRF when available. In case the corrected calcium is not provided but both the total calcium and the serum albumin are available, the corrected calcium will be calculated as

corrected calcium (mmol/L) = total calcium (mmol/L) + $0.02 \times [40 - \text{serum albumin } (g/L)]$

Therefore, the derived corrected calcium parameter will consider the values collected in the eCRF for corrected calcium if available, otherwise the values will be derived using the formula above when possible.

For the reference ranges of the derived corrected calcium, the following rules will be applied for each participant:

- if corrected calcium is measured at least once and the reference ranges are available, the reference ranges from the first measurement will be used for all the collected or derived values;
- if corrected calcium is never measured and/or the reference ranges are not available, the reference ranges reported in Section 18.3 will be used for all the collected or derived values.

All the calcium parameters collected in the eCRF as well as the derived corrected calcium will be listed. Only the total calcium and the derived corrected calcium will be tabulated as appropriate.

Liver function tests: Alanine aminotransferase (ALT), aspartate aminotransferase (AST), and total bilirubin (TBILI) are used to assess possible drug induced liver toxicity. The ratios of the test result over the upper limit of normal (ULN) will be calculated and classified for these three parameters during the on-treatment periods.

The summary of liver function tests will include the following categories. The number and percentage of participants with each of the following during the on-treatment periods will be summarized by treatment group:

- ALT < 3×ULN, ALT \ge 3×ULN, ALT \ge 5×ULN, ALT \ge 10×ULN, ALT \ge 20×ULN
- AST < 3×ULN, AST \ge 3×ULN, AST \ge 5×ULN, AST \ge 10×ULN, AST \ge 20×ULN

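### SAP 15.3.1 puts deaths after the switch to tepotinib plus osimertinib in the monotherapy column without a split, and its 30-day row, read with SAP 9.2, runs from the last monotherapy dose

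*SAP*

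**What the plan says.** Protocol 4.1 lets a monotherapy participant move to the combination once the investigator reports progression and the IRC verifies it. SAP 9.3, Table 3, divides a switcher's time at the first osimertinib dose. Period 1 ends there. Period 2 runs until 30 days after the last combination dose, or to cut-off or death if earlier. Footnote a sets a default that other sections may override: "data from Period 1 will contribute to tables, figures and listings whereas data from Period 2 to study discontinuation will only be listed".

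SAP 15.3.1 departs from that default. It tabulates "Deaths from both Period 1 and Period 2 (see Table 3), deaths within 30 days after last dose of study treatment", overall and by primary reason. Period appears again only in the text on the individual listing: "Deaths that occured during Period 2 will be flagged". SAP 8.1.2, Table 1, gives the monotherapy columns for safety as "Tepotinib 500mg: T+, L+, Combined (T+ and/or L+), Other, Total Tepo".

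For the dose anchor, SAP 9.2 says that study treatment "indicates tepotinib only in the monotherapy arm" and defines its end date: "for the monotherapy arm it will be the last date of administration of tepotinib as monotherapy". Table 3 footnote c has a separate rule for switchers: "The last dose of the combination treatment is considered as the last dose of tepotinib or osimertinib, whichever is later". SAP 15.3.1 does not use it.

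Protocol 9.4.2 asks for all deaths, and for deaths within 30 days of the last dose of study intervention. Protocol Section 6 defines study intervention to include both the combination and the monotherapy.

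**The concern.** The safety of tepotinib monotherapy is a secondary objective in its own right (Protocol 3, SAP 5). A reader will take the monotherapy column of the death table as a description of that regimen. Switching happens at progression, so deaths after it are foreseeable, and these participants were by then taking two drugs.

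Two things could mislead. First, the table shows one total per column, so deaths before and after osimertinib was added cannot be told apart. Second, the 30-day row is the usual proxy for deaths on or near treatment. If its clock starts at the last monotherapy dose, a switcher's deaths are sorted by how long the combination lasted and not by how close death was to the last drug taken.

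**Working it through.** No figure in the plan is at stake. The check sets the definitions side by side and then adds illustrative arithmetic.

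**1. Where a post-switch death is counted**

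| Output for the monotherapy arm | Time covered for switchers | Source |
|---|---|---|
| Main TEAE tables, including TEAEs leading to death | TEAEs assigned to Period 1 | SAP 15.2.1, 15.2.2 |
| Worst graded laboratory values | Period 1 | SAP 15.4 |
| Death table | Periods 1 and 2 together | SAP 15.3.1 |
| Death listing | Both, with Period 2 flagged | SAP 15.3.1 |

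The pooled Period 1 and 2 adverse event tables in SAP 15.2.2 are extra outputs, made only if at least 6 participants switch. The death table and the fatal-TEAE table therefore share a column heading but cover different exposure. A death attributed to osimertinib can stand in the column for tepotinib alone. Protocol 9.4.2 takes the opposite line for adverse events: the monotherapy window closes at the switch, and later events are described separately.

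**2. The 30-day row**

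Let L be the days from the last monotherapy dose to the last combination dose, and D the days from the last combination dose to death.

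- Anchor in SAP 9.2 (last monotherapy dose): counted if L + D ≤ 30.
- Anchor in Table 3 footnote c (last combination dose): counted if D ≤ 30.

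Assumed timings:

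| L | D | L + D | Counted under SAP 9.2 | Counted under footnote c |
|---|---|---|---|---|
| 7 | 20 | 27 | yes | yes |
| 14 | 5 | 19 | yes | yes |
| 14 | 20 | 34 | no | yes |
| 42 | 5 | 47 | no | yes |

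The 42/5 case is a death 5 days after the last drug taken, and the row misses it. The 14/5 case is counted in the monotherapy 30-day row, although osimertinib had been added. By Table 3, Period 2 closes no later than 30 days after the last combination dose. Every Period 2 death is therefore within 30 days of that dose by construction, yet only those with L + D ≤ 30 enter the row.

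The listing has its own flag for death within 30 days of the last study treatment, and it inherits the same anchor.

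**3. Size**

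Protocol 9.2 plans 12 monotherapy participants. One death is 1/12 = 8.3 points of the T+ column.

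The documents give no number of switchers and no death rate after the switch. For an assumed s switchers with risk q of death in Period 2, the expected addition is s × q deaths, or 100 × s × q / 12 points:

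- s = 3, q = 0.10: 0.3 deaths, 2.5 points.
- s = 6, q = 0.25: 1.5 deaths, 12.5 points.
- s = 12, q = 0.50: 6 deaths, 50 points.

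The width of this range reflects what the documents leave open; it is not a forecast.

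**The case against.** **The count is explicit and follows the protocol.** Protocol 9.4.2 requires all deaths, SAP 15.3.1 says openly that both periods are included, Period 2 deaths are flagged, and the primary-reason rows separate progression, tepotinib, osimertinib, both and neither. All of this stands, and no death should be dropped. But a reason row records a judgement of cause; it does not show what the participant was taking, and the flag is described with the listing, not the table.

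**The 30-day anchor is inferred.** SAP 15.3.1 does not cite 9.2. Switchers continue tepotinib, so their last tepotinib dose could be read as falling in Period 2. Table 3 uses the last dose of study treatment only for the combination and no-switch columns. This partly stands: the reading here joins two sections. However, 9.2 is the only place where the SAP defines the end of study treatment for this arm, and it specifies tepotinib as monotherapy. The alternative would still put combination deaths, unmarked, in the monotherapy 30-day row.

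**The safety analysis is descriptive, and 12 is only the T+ target.** Both stand. Participants who are not centrally T+ can make the total monotherapy column larger than 12, and the 8.3-point step applies to the T+ column only.

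**The liver outputs.** A reader might infer that the liver table also counts post-switch events, because SAP 15.4 says "The number and percentage of participants with each of the following during the on-treatment periods will be summarized by treatment group" and 9.3 defines both periods under that heading. The documents do not support this. The opening of SAP 15 keeps switchers' laboratory results after Period 1 out of tables and figures unless stated otherwise, and the liver text never names Period 2. Where the SAP wants Period 2 in a table, as in 15.2.2 and 15.3.1, it says so. The same general rule covers the eDISH plots.

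**Conclusion.** The point holds for the death table and its 30-day row and flag.

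- Mixing the two periods in the monotherapy column follows directly from SAP 15.3.1 and Table 1.
- The 30-day problem rests on reading 15.3.1 with the definition in 9.2. On that reading it departs from the protocol, whose study intervention covers both regimens.

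The effect is about 8.3 points of the T+ monotherapy column per post-switch death if n = 12. The total depends on the number of switchers and their death rate, neither of which is given.

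A reader might go further and conclude that monotherapy safety as a whole is misreported. That is too broad. The main adverse event, fatal-TEAE and graded laboratory tables keep to Period 1, the reason rows carry attribution, and the liver table and eDISH plots are not shown to be wrong. This should be put right in the SAP, but it concerns one table and one listing flag.

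**What to change.** In SAP 15.3.1:

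1. Keep every death, but split the monotherapy-arm rows into two blocks: deaths before the first osimertinib dose or in participants who never switched, and deaths on or after that dose.
2. For deaths in the second block, anchor the 30-day row and the listing flag on the last combination dose as defined in Table 3 footnote c. Leave these deaths out of the monotherapy 30-day row.
3. State the anchor in 15.3.1 itself, so that it does not depend on 9.2.

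Optionally, reword the on-treatment periods in the liver text of 15.4 to Period 1, in line with the general rule in SAP 15. This only clarifies the wording.

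The cost is a few lines of SAP text and one extra row block in one table. The SAP already uses the dates of death, of the first osimertinib dose and of the last dose of each drug, so no new data are needed.

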15.3.2 Serious Adverse Events

Please see Section 15.2.2 for the analysis of serious TEAEs.

A listing of serious TEAEs will also be provided.

15.3.3 Other Significant Adverse Events

Please see Section 15.2.2 for the analysis of AEs of special interest.

15.4 Clinical Laboratory Evaluation

Laboratory assessments such as hematology and coagulation, biochemistry, urinalysis and other screening tests (e.g., pregnancy tests) will be performed by local laboratories.

Laboratory results will be classified according to the NCI-CTCAE criteria version 5.0. Additional laboratory results that are not part of NCI-CTCAE will be presented according to the categories: below normal limit, within normal limits and above normal limit (according to the laboratory normal ranges).

Baseline and change from baseline definitions are in Section 9.4.

Values below the detection limit will be imputed by half of the detection limit.

If a text value with an "> x" is reported it will be analyzed as +1 significant digit, e.g., "> 7.2 mmol" will be analyzed as 7.3.

Quantitative data will be summarized using descriptive statistics (n, mean, SD, median, Q1, Q3, minimum, and maximum) of actual values and absolute changes from baseline to each scheduled visit over time. Only baseline and on-treatment values will be summarized. In addition, with the exception of the baseline, end of treatment and safety follow-up visits, all the other visits will be presented if the data are available for at least 6 participants overall.

Qualitative data based on reference ranges will be described according to the categories Low, Normal, and High (Hematology, Biochemistry and Coagulation). For qualitative data of urinalysis measurements, the raw classifications Normal, Trace/+, ++, +++, ++++ will be used instead. Results from the urinalysis microscopic examination (Erythrocytes, Leukocytes, Epithelial cells, Bacteria, Crystals and Casts) will only be listed. Abnormalities classified according to NCI-CTCAE toxicity grading version will be described using the worst on-treatment grade. Measurements from both scheduled and unscheduled visits performed during Period 1 (see Table 3) will be considered for the worst on-treatment grade derivation. For those parameters which are graded with two directions of toxicities such as potassium (hypokalemia/hyperkalemia), the toxicities will be summarized separately. Low direction toxicity (e.g., hypokalemia) grades at baseline and post baseline will be set to 0 when the variables are derived for summarizing high direction toxicity (e.g., hyperkalemia), and vice versa. For the biochemistry parameters alkaline phosphatase, alanine aminotransferase, aspartate aminotransferase, total bilirubin, gamma glutamyl transferase and creatinine, the on-treatment grading is dependent upon the normality or abnormality of the baseline value; in such cases, the worst on-treatment grading will also be displayed according to the baseline grading (normal vs abnormal).

Derived Biochemistry Parameters

Creatinine clearance

24-hour creatinine clearance and/or creatinine clearance (Cockcroft-Gault) measurements are only collected at screening. Therefore, in order to monitor the renal impairment during the study, creatinine clearance (mL/min) will be calculated by the Cockcroft-Gault formula as

$$\frac{\{[140 - age(year)] \times weight(kg)\}}{72 \times serum \ creatinine} \begin{pmatrix} mg \\ dL \end{pmatrix}} \times [0.85 \ for \ females]$$

Age at the date of the creatinine collection (only the integer part should be considered) and the closest measurement of weight to the date of creatinine collection will be used. See Section 9.6 for the conversion of serum creatinine from umol/L to mg/dL.

For the reference ranges, the following rules will be applied for each participant:

- if creatinine clearance (Cockcroft-Gault) is measured at screening and the reference ranges are available, these reference ranges will be used for all the collected or derived values;
- if creatinine clearance (Cockcroft-Gault) is not measured at screening and/or the reference ranges are not available, the reference ranges reported in Section 18.3 will be used for all the collected or derived values.

The derived creatinine clearance will be analysed and presented as a non-gradable parameter in tables and listings. The creatinine clearance values collected only at the screening visit and reported in the eCRF will only be listed.

Calcium

Total calcium, corrected calcium and ionized calcium will be collected in the eCRF when available. In case the corrected calcium is not provided but both the total calcium and the serum albumin are available, the corrected calcium will be calculated as

corrected calcium (mmol/L) = total calcium (mmol/L) + $0.02 \times [40 - \text{serum albumin } (g/L)]$

Therefore, the derived corrected calcium parameter will consider the values collected in the eCRF for corrected calcium if available, otherwise the values will be derived using the formula above when possible.

For the reference ranges of the derived corrected calcium, the following rules will be applied for each participant:

- if corrected calcium is measured at least once and the reference ranges are available, the reference ranges from the first measurement will be used for all the collected or derived values;
- if corrected calcium is never measured and/or the reference ranges are not available, the reference ranges reported in Section 18.3 will be used for all the collected or derived values.

All the calcium parameters collected in the eCRF as well as the derived corrected calcium will be listed. Only the total calcium and the derived corrected calcium will be tabulated as appropriate.

Liver function tests: Alanine aminotransferase (ALT), aspartate aminotransferase (AST), and total bilirubin (TBILI) are used to assess possible drug induced liver toxicity. The ratios of the test result over the upper limit of normal (ULN) will be calculated and classified for these three parameters during the on-treatment periods.

The summary of liver function tests will include the following categories. The number and percentage of participants with each of the following during the on-treatment periods will be summarized by treatment group:

- ALT < 3×ULN, ALT \ge 3×ULN, ALT \ge 5×ULN, ALT \ge 10×ULN, ALT \ge 20×ULN
- AST < 3×ULN, AST \ge 3×ULN, AST \ge 5×ULN, AST \ge 10×ULN, AST \ge 20×ULN
- (ALT and AST) < 3×ULN, (ALT or AST) \ge 3×ULN, (ALT or AST) \ge 5×ULN, (ALT or AST) \ge 10×ULN, (ALT or AST) \ge 20×ULN
- TBILI < $2 \times ULN$, TBILI $\ge 2 \times ULN$
- Concurrent ALT \ge 3×ULN and TBILI \ge 2×ULN
- Concurrent AST \ge 3×ULN and TBILI \ge 2×ULN
- Concurrent (ALT or AST) \ge 3×ULN and TBILI \ge 2×ULN
- Concurrent (ALT or AST) \ge 3×ULN and TBILI \ge 2×ULN and Alkaline Phosphatase (ALP) > 2×ULN
- Concurrent (ALT or AST) \ge 3×ULN and TBILI \ge 2×ULN and ALP \le 2×ULN or missing.

Concurrent measurements are those occurring on the same date.

Categories will be cumulative, i.e., a participant with an elevation of AST $\ge 10 \times ULN$ will also appear in the categories $\ge 5 \times ULN$ and $\ge 3 \times ULN$.

Liver function elevation and possible Hy's Law cases will be summarized using frequency and percentage. An evaluation of Drug-Induced Serious Hepatotoxicity (eDISH) plot will also be created by graphically displaying:

- Peak serum ALT(/ULN) versus peak total bilirubin (/ULN) including reference lines at ALT = 3×ULN and total bilirubin = 2×ULN
- Peak serum AST(/ULN) versus peak total bilirubin (/ULN) including reference lines at AST = 3×ULN and total bilirubin = 2×ULN.

In addition, a listing of all TBILI, ALT, AST and ALP values for participants with a post-baseline TBILI $\ge 2 \times ULN$, ALT $\ge 3 \times ULN$ or AST $\ge 3 \times ULN$ will be provided.

Parameters with NCI-CTC grades available:

Laboratory toxicities will be tabulated (count and percentage) for each gradable parameter by the worst on-treatment CTCAE grade. Shifts from baseline to worst CTCAE grade during the on-treatment period will also be tabulated. The denominator to calculate percentages for each laboratory parameter is the number of participants in each analyzed group. Participants without baseline or on-treatment post-baseline results for a given parameter will be presented in the "Missing" category and will contribute to the denominator.

Please see Section 18.1 for a list of the CTCAE-gradable parameters.

Parameters with NCI-CTC grades not available:

Laboratory abnormalities will be tabulated (count and percentage) for each non-gradable parameter by the worst on-treatment abnormality. For each parameter, shift tables from baseline to the maximum post-baseline as well as the minimum post-baseline on-treatment value will be presented. The denominator to calculate percentages for each laboratory parameter is the number of participants in each analyzed group. Participants without baseline or post-baseline results for a given parameter will be presented in the "Missing" category and will contribute to the denominator.

The following figures will be provided for each above-mentioned test:

- Boxplots of the laboratory values by timepoint
- Boxplots of the change from baseline by timepoint.

Boxplots for laboratory parameters where toxicity grades are defined based on the ratio of the parameter values and the upper limit of normal (ULN) will not be displayed using the unit of measurement but instead using the ratio of the measured value over ULN. This comprises ALP, ALT, AST, bilirubin, creatinine.

The listings of laboratory results will be provided for all laboratory parameters. The listings will be sorted by parameter and assessment dates or visits for each participant. Laboratory values that are outside the normal range will be flagged in the data listings, along with corresponding normal ranges and CTCAE grades. The coagulation parameter Activated Partial Thromboplastin Time/Standard Ratio will only be listed as it is only reported for a restricted number of sites.

Results from pregnancy tests, both serum and urine, collected on the "Pregnancy Test" eCRF page will be listed together with Follicle-stimulating Hormone and Estradiol values collected at the screening visit.

